**Statistical Analysis Plan Revision History**

Version	Date	Author(s)	Summary of Changes/Comments
Version 0.1	June 15, 2017	██████████	First version
Version 1.0	August 19, 2017	██████████	Final version

## 1 LIST OF ABBREVIATIONS AND TERMS

Abbreviation	Term
°C	Celsius
°F	Fahrenheit
ADT	Androgen Deprivation Therapy
AE	Adverse Event
ALP	Alkaline phosphatase
ALT	Alanine transaminase
AST	Aspartate transaminase
BHR	BHR Pharma, LLC
BHR-200	Transdermal 17-β estradiol gel (all strengths currently in development)
BMI	Body Mass Index
BSAP	Alkaline Phosphatase, Bone Specific
BUN	Blood urea nitrogen
CRF	Case report form
dL	Deciliter
ECG	Electrocardiogram
EOS	End of Study (visit)
EPIC	Expanded Prostate Cancer Index Composite
ET	Early Termination (visit)
FDA	U.S. Food and Drug Administration
FSH	Follicle-Stimulating Hormone
g	Gram
GCP	Good Clinical Practice
GnRH	Gonadotropin-Releasing Hormone
HbA1c	Glycated haemoglobin
ICH	International Conference on Harmonisation
kg	Kilogram
LDH	Lactate dehydrogenase
LH	Luteinizing Hormone
mg	Milligram
mL	Milliliter
mmHg	Millimeter of mercury
ng	Nanogram
OTC	Over the counter
pg	Picogram

PK	Pharmacokinetic
pmol	Picomole
PSA	Prostate-Specific Antigen
SAE	Serious Adverse Event
SAP	Statistical analysis plan
SHBG	Sex Hormone Binding Globulin
µg	Microgram
U.S.	United States
WHO	World Health Organization
	
For the purpose of consistency, the following units will be used throughout this document:
 
Estradiol: pg/mL (1 pmol/L= 0.2724 pg/mL)  Testosterone: ng/dL (1 nmol/L = 28.82 ng/dL)

## 3 STUDY OBJECTIVES

### 3.1 Primary objective

- To evaluate the safety and efficacy of three different doses of BHR-200 (0.36% transdermal estradiol gel) compared to placebo for the maintenance of testosterone (T) suppression in men with advanced androgen-sensitive prostate cancer.

### 3.2 Secondary objectives

- To select the dose(s) for a subsequent Phase 3 trial.

## 4 STUDY OVERVIEW

### 4.1 Study design

This was a multi-center, randomized, double-blind, placebo-controlled, dose-finding study in men with advanced androgen-sensitive prostate cancer. Patients participated in a 24-week double-blind treatment period and were allowed to continue treatment with their assigned study drug for up to 52 weeks as long as they remained chemically castrated. Patients who gave informed consent had screening evaluations, and if fulfilling the entry criteria, were randomized to one of 4 treatment groups: 1mL, 2mL or 3mL of 0.36% BHR-200 (transdermal estradiol gel) or placebo. Study drug was initiated on the day (+/- 5 days) they would be scheduled to receive the next GnRH agonist depot injection. Patients were offered low-dose radiation to aid in the prevention of gynecomastia. Patients applied the study drug once per day. The first dose was applied under the supervision of the

PI/designee. Subsequent doses were self-administered daily by the patient until one of the following occurred:

- he was no longer chemically castrated as demonstrated by testosterone levels greater than or equal to 50 ng/dL,
- a rise in PSA over baseline of  $\geq 0.5$  ng/mL was observed,
- he had completed 24 weeks of double blind treatment, and elected not to continue into the extension period, or
- he had completed 52 weeks of study drug administration.

At the conclusion of study participation, patients were advised to resume standard of care treatment under the supervision of their healthcare provider. While on treatment, patients were evaluated at Day 1, every 2 weeks, for the first 24 weeks, and every 4 weeks thereafter, with a final post-treatment follow-up visit 2 weeks (+/- 2 days) post last dose administration.

## **4.2 Study Drug Administration**

The 0.36% BHR-200 gel formulation contains 3.6 mg/g estradiol in a clear, colorless, absorptive hydroalcoholic gel base formulated to provide continuous release of estradiol. BHR-200 was supplied in a non-aerosol canister with a 1mL metered-dose pump. A single pump actuation delivered 3 mg of estradiol in 0.87 g of gel. The gel was applied to clean, dry, intact skin of the upper arms and shoulders.

## **4.3 Sample Size and Power Analysis**

The planned sample size was 120 male patients. Assuming the response rate (the proportion of patients maintaining castrate levels of T ( $T < 50$  ng/dL)) for the placebo group was 5%, the response rate for the low dose group of BHR-200 was 50%, the response rate for the mid dose group was 80%, and the response rate for the high dose group of BHR-200 was 95%, 30 patients per treatment group provided at least 90% power to detect the difference in proportion of patients maintaining castrate levels of T ( $T < 50$  ng/dL) between any dose of BHR-200-treated patients and the placebo-treated patients using a two-sided Fisher-Exact test with a 5% significance level.

However, this study was discontinued prematurely by the sponsor. A final total of 34 study subjects will be included in the analyses.

## 5 ANALYSIS ENDPOINTS

### 5.1 Efficacy Endpoints

#### Primary Efficacy Endpoint:

The primary efficacy endpoint is the response rate (the proportion of patients maintaining castrate levels of T ( $T < 50$  ng/dL)). The primary analysis on the primary efficacy endpoint is to compare the response rate from each of the 3 BHR-200 dose levels against the response rate for the placebo-treated patients at Week 12.

#### Secondary Efficacy Endpoints:

- (1) The response rate at Week 24. The same statistical analysis method that applied to Week 12 analysis will be used for Week 24.
- (2) The Kaplan-Meier curve for time to  $T > 50$  ng/dL through Week 12 for each treatment group.
- (3) The Kaplan-Meier curve for time to  $T > 50$  ng/dL through Week 24 for each treatment group.

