Primary	To evaluate the safety and efficacy of three different doses of BHR-200 (0.36% transdermal estradiol gel) compared to placebo for the maintenance of testosterone (T) suppression in men with advanced androgen-sensitive prostate cancer.
Secondary	To select the dose(s) for a subsequent Phase 3 trial.
Study Endpoints	
Primary	Maintenance of T suppression, defined as the absence of any T level measurement greater than or equal to 50 ng/dL during Weeks 4 to 12 of double blind treatment.
Secondary	Maintenance of T suppression, defined as the absence of any T level greater than or equal to 50 ng/dL during Weeks 4-24 of double blind treatment. Incidence and severity of adverse events with special attention given to thromboembolic events. Serum concentrations of: follicle-stimulating hormone (FSH), luteinizing hormone (LH), sex hormone binding globulin (SHBG), and prostate-specific antigen (PSA).
Study Design	
Methodology	This is a multi-center, randomized, double-blind, placebo-controlled, dose-finding study in men with advanced androgen-sensitive prostate cancer. Patients who give informed consent will have screening evaluations, and if fulfilling the entry criteria, will be randomized to one of 4 treatment groups: 1 mL, 2mL or 3mL of 0.36% BHR-200 (transdermal estradiol gel) or placebo. Study drug will be initiated on the day (+/- 5 days) they would be scheduled to receive the next GnRH agonist depot injection. Patients will be offered low-dose radiation to aid in the prevention of gynecomastia. Patients will apply the study drug once per day. The first dose will be applied under the supervision of the PI/designee. Subsequent doses will be self-administered daily by the patient until one of the following occurs:

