
Sample Size Determination
	
The sample size for this dose-finding study is a total of 120 patients. The sample size is based on the following assumptions:
 
 • the response rate (the proportion of patients maintaining castrate levels of T ($T < 50$ ng/dL) for the placebo group is 5%, • the response rate of the low dose group of BHR-200 is 50%, • the response rate of the mid dose group is 80%, and • the response rate of the high dose group of BHR-200 is 95%. 
Thirty patients per treatment group will provide at least 90% power to detect the difference in proportion of patients maintaining castrate levels of T ($T < 50$ ng/dL) between any dose of BHR-200-treated patients and the placebo-treated patients using a two-sided Fisher-Exact test with a 5% significance level.

Statistical Methods
	
The primary efficacy endpoint is the response rate which is defined as the proportion of patients maintaining castrate levels of T ($T < 50$ ng/dL). The responder rate will be compared for each of the 3 BHR-200 dose levels against the responder rate for the placebo-treated patients at Week 12. The Cochran–Mantel–Haenszel (CMH) statistics will be used to compare 2 responder rates of 2 treatment groups adjusted for appropriate baseline characteristics.
 
The following comparisons will be made between active dose levels and placebo, and the study will be considered successful if the first comparison reaches a significance level of $p < 0.05$. Subsequent comparisons will be considered significant only if they reach a significance level of $p < 0.05$ in addition to the comparison prior to it.
 
 • High dose vs. placebo • Mid dose vs. placebo • Low dose vs. placebo • Low dose vs. high dose • Mid dose vs. high dose • Low dose vs. mid dose 
Secondary efficacy endpoints will include:
 
(1) The proportion of the responder rate at Week 24. The same statistical analysis method that applied to Week 12 analysis will be used for Week 24.

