8.7 Efficacy Analysis

The primary efficacy endpoint is the response rate (the proportion of patients maintaining castrate levels of T ($T < 50$ ng/dL)). The primary analysis on the primary efficacy endpoint is to compare the response rate from each of the 3, BHR-200 dose levels against the response rate for the placebo-treated patients at Week 12 using the Cochran–Mantel–Haenszel (CMH) statistics adjusted for appropriate baseline characteristics.

The following comparisons will be made between active dose levels and placebo, and the study will be considered successful if the first comparison reaches a significance level of $p < 0.05$. Subsequent comparisons will be considered significant only if they reach a significance level of $p < 0.05$ in addition to the comparison prior to it.

- High dose vs. placebo
- Mid dose vs. placebo
- Low dose vs. placebo
- Low dose vs. high dose
- Mid dose vs. high dose
- Low dose vs. mid dose

Secondary efficacy endpoints will include:

- (4) The proportion of the response rate at Week 24. The same statistical analysis method that applied to Week 12 analysis will be used for Week 24.
- (5) The Kaplan-Meier curve for time to $T > 50$ ng/dL at Week 12 for each treatment group.
- (6) The Kaplan-Meier curve for time to $T > 50$ ng/dL at Week 24 for each treatment group.

For the time-to-event analysis, the log-rank test and the Wilcoxon test will be used to compare the median time to event. In addition, a Cox proportional hazard model will be used to analyze the time-to-event, and the model will be stratified by the appropriate baseline characteristics. Treatment effect will be tested for the hazard ratio using the Wald Chi-squared test. In addition, the 95% confidence interval for the hazard ratio (HR) will be estimated

All other efficacy parameters (e.g., FSH, LH, SHBG, and PSA) will be summarized by treatment group at each study visit using descriptive statistics. Serum levels of estradiol and estrone will be summarized by treatment group at each study visit using descriptive statistics. The EPIC-Hormonal Assessment and the EPIC-Sexual Assessment will be summarized by treatment group at each study visit using descriptive statistics.

9.0 (Serious) Adverse Event Collection and Reporting

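### SAP 5.1 sets the Kaplan-Meier event at T above 50 ng/dL with no Week 4 start, although failure is T of 50 or more from Week 4, so curve and response rate can classify a man differently

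*SAP*

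**What the plan says.** **Response.** SAP 5.1 gives the primary endpoint as "the proportion of patients maintaining castrate levels of T ( $T < 50$ ng/dL" and compares each dose with "the response rate for the placebo-treated patients at Week 12". It states no window. The window is in the endpoint rows of the Protocol Synopsis: "the absence of any T level measurement greater than or equal to 50 ng/dL during Weeks 4 to 12 of double blind treatment" for the primary endpoint and "the absence of any T level greater than or equal to 50 ng/dL during Weeks 4-24 of double blind treatment" for the secondary one. The Synopsis methods row uses the same Week 12 shorthand as the SAP ("against the responder rate for the placebo-treated patients at Week 12"), but there the endpoint rows supply the window.

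**KM event.** SAP 5.1 uses a strict inequality for both curves: "The Kaplan-Meier curve for time to $T > 50$ ng/dL through Week 12 for each treatment group" and "The Kaplan-Meier curve for time to $T > 50$ ng/dL through Week 24 for each treatment group". Protocol 8.7 does the same ("The Kaplan-Meier curve for time to $T > 50$ ng/dL at Week 12 for each treatment group"). The KM items in the Synopsis methods row use 50 or more. None of these texts gives a start week.

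**Withdrawal and sampling.** Protocol 3.0 and 4.3 withdraw a man for T of 50 or more once 4 weeks of double-blind treatment have passed, and 4.3 labels this treatment failure. T is measured every 2 weeks, including at Week 2 (Protocol 7.3).

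**Analysis.** SAP 11 drops inferential efficacy analyses but keeps descriptive summaries of the primary and secondary endpoints. SAP 4.3 gives 34 men in total.

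**The concern.** The response rate and the KM curve are meant to describe the same thing, loss of castrate testosterone, as a proportion and over time. Under the present definitions they can disagree about one man in two ways.

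- **Threshold.** A value of exactly 50 from Week 4 is failure for response and for withdrawal, but not a KM event. The man leaves the trial because he failed, and the curve censors him at that point. Such censoring is informative and makes the curve look better than it should.
- **Start.** A Week 2 value above 50 is a KM event, although the Synopsis window has not opened and Protocol 4.3 keeps the man on treatment. If he is below 50 from Week 4 on, he is a responder with a KM event.

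No p-value is at stake. What is at stake is the consistency of two descriptive summaries by dose in a small trial whose secondary objective is still to select a Phase 3 dose (SAP 3.2).

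**Working it through.** **The plan's own figure.** SAP 4.3 claims at least 90% power with 30 men per arm (two-sided Fisher exact test, 5% level). Exact enumeration gives 98.2% for 5% against 50%, and more than 99.9% for 5% against 80% or 95%, so the claim is met. It rests on the response rate and not on the KM event, so this point does not touch it.

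**Scheduled post-baseline T values.** Through Week 12 there are 6 (Weeks 2, 4, 6, 8, 10, 12), of which 5 lie in the Weeks 4-12 window. Through Week 24 there are 12, of which 11 lie in the Weeks 4-24 window. Only Week 2 falls outside.

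**Rules applied to example series.** The values are illustrative. Response uses the Synopsis window. The last column dates the event at the first T of 50 or more from Week 4.

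| T series (ng/dL) | Responder | KM event, SAP 5.1 | KM event, proposed |
|---|---|---|---|
| 50 at Week 8 only | no | none | Week 8 |
| 60 at Week 2, below 50 after | yes | Week 2 | none |
| 60 at Weeks 2 and 4 | no | Week 2 | Week 4 |
| 51 at Week 8 | no | Week 8 | Week 8 |
| never 50 or more | yes | none | none |
| 50 at Week 2 only | yes | none | none |

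The first two rows are true disagreements. In the third, both analyses record a failure, but SAP 5.1 dates it before the window opens. With the proposed event, KM status and responder status agree in all six rows.

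**Size of one man.** The documents do not give the arm sizes. Assuming an equal split, 34/4 = 8.5, so arms hold 8 or 9 men. All other men are taken as below 50 and followed to Week 12.

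- *Exactly 50 at Week 8, then withdrawn.* Response is (n − 1)/n: 7/8 = 87.5% or 8/9 = 88.9%. KM at Week 12 under SAP 5.1 is 100%, since he is censored. With an event at 50 or more, KM is also 87.5% or 88.9%.
- *Above 50 at Week 2 only.* Response is n/n = 100%. KM under SAP 5.1 is (n − 1)/n = 87.5% or 88.9%.

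The gap is 100/n points in either case: 12.5 for n = 8 and 11.1 for n = 9. If arms ranged from 6 to 11 men (an assumption), it would run from 100/6 = 16.7 to 100/11 = 9.1.

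**The case against.** **The threshold needs an exact tie.** The documents show no value of exactly 50 and give no reporting precision for the assay. This stands and limits the effect. It does not remove the error: the strict sign conflicts with the SAP's own response rule, the Synopsis and the withdrawal rule. A symbol lost in PDF conversion is unlikely, because the strict sign appears four times across two documents while the other sign was read correctly elsewhere.

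**The start-week conflict draws on two documents.** SAP 5.1 states no window for response either. Read alone, a man above 50 at Week 2 could count as not maintaining castrate levels and also as a KM event, with no conflict. Nor does the SAP depart from the protocol here, since the Synopsis KM items and Protocol 8.7 also lack a start. A curve from first dose is a legitimate summary in itself. Much of this stands: the disagreement arises only when the Synopsis window governs response. That window is, however, the only explicit one the documents give, and Protocol 4.3 agrees with it. Protocol 8.1 gives the SAP precedence over the protocol's statistical section, so the SAP is where the window should be stated.

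**Side-by-side reading is inferred.** SAP 11 names no KM display and no paired table. True, but the curves are listed secondary endpoints and SAP 11 keeps those endpoints.

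**A stronger reading is not supported.** The Synopsis methodology and SAP 4.1 describe stopping at T of 50 or more without a start week. A reader might infer that a man withdrawn at Week 2 would have no value in the window and, with no imputation under SAP 7.2, no response status. Protocol 3.0 and 4.3, which carry the operative rule, both limit this withdrawal to after 4 weeks; the other two texts are summaries. The case needs a site to act against the detailed rule, and even then the high value has been observed.

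**Conclusion.** The point holds as a minor one. The threshold error is certain on the text: SAP 5.1 and Protocol 8.7 set the KM event above 50, while response, the Synopsis endpoints and KM items, and withdrawal all treat 50 itself as failure. The missing Week 4 start is a smaller matter. It produces a disagreement only if response is judged by the Synopsis window and the man is below 50 from Week 4 on; otherwise it can only move the date of a KM event earlier.

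The number of men affected is unknown. One man is worth 11.1 to 12.5 points if the arms hold 8 or 9 men, which is an illustration on assumed arm sizes and not an estimate of bias. A reader might infer that a treatment comparison or the stated power is compromised. It is not: SAP 11 drops inferential efficacy analyses, and the power calculation uses the response rate.

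**What to change.** In SAP 5.1:

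1. Define a responder as a man with no T of 50 ng/dL or more in Weeks 4-12, and in Weeks 4-24 for the secondary endpoint.
2. Define the KM event, for both curves, as the first T of 50 ng/dL or more at or after the Week 4 visit.
3. List in the clinical study report every man with a Week 2 T of 50 ng/dL or more, so that early rises stay visible although neither analysis counts them.

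The stopping rule needs no change. Because the SAP takes precedence (Protocol 8.1), Protocol 8.7 need not be amended. The cost is a few sentences, a re-derivation of response status and of KM event and time from T values already collected, and one listing. No new data are needed.

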#### Exploratory Endpoints:

All other efficacy parameters (e.g., FSH, LH, SHBG, and PSA) will be summarized by treatment group at each study visit using descriptive statistics. Serum levels of estradiol and estrone will be summarized by treatment group at each study visit using descriptive statistics. The Expanded Prostate Cancer Index Composite (EPIC)-Hormonal Assessment and the EPIC-Sexual Assessment will be summarized by treatment group at each study visit using descriptive statistics.

### 5.3 Pharmacokinetic Endpoints

The following pharmacokinetic data was collected and evaluated at each visit: serum estradiol and estrone.

## 6 ANALYSIS POPULATIONS

### 6.1 Intent-to-treat (ITT) population

The Intent-to-treat (ITT) population will contain all patients who are randomized into the study. All efficacy parameters will be analyzed using the ITT population. In the case of a patient who was randomized but did not take the study drug, the analysis will be done for this patient using the randomized treatment.

### 6.2 Safety population

The Safety population will contain all patients who receive at least one dose of study drug. All safety parameters will be analyzed using the Safety population.

## 7 DATA AND ANALYSIS CONVENTIONS

Post-text tables and listings will be prepared in accordance with the current ICH Guidelines. The information and explanatory notes to be provided in the “footer” or bottom of each table and listing will include the following information:

1. Date and time of output generation;
2. SAS program name, including the path that generates the output;
3. Any other output-specific details that require further elaboration.

In general, tables will be formatted with a column for each treatment group. The tables for baseline data will be formatted with an additional column displaying the findings for all subjects combined. In general, Row entries in tables are made only if data exists for at least one subject (*i.e.*, a row with all zeros will not appear). The exception to this rule applies to tables that list the termination status of subjects (*e.g.*, reasons for not completing the study). In this case, zeros will appear for study termination reasons that no subject satisfied. The summary tables clearly indicate the number of subjects to which the data apply and unknown or not performed are distinguished from missing data.

Specific algorithms are discussed for imputing missing or partially missing dates, if deemed appropriate, under specific data topics. Imputed or derived data are flagged in the individual subject data listings. Imputed data are not incorporated into any raw or primary datasets. These data are retained in derived (or analysis) datasets.

This section details general conventions to be used for the statistical analyses. The following conventions will be applied to all data presentations and analyses.

- Summary statistics will consist of the number and percentage of responses in each level for categorical variables, and the sample size (n), mean, median, standard deviation (SD) and range (*i.e.* minimum and maximum values) for continuous variables.
- All mean and median values will be formatted to one more decimal place than the measured value. Standard deviation values will be formatted to two more decimal places than the measured value. Minimum and maximum values will be presented with the same number of decimal places as the measured value.
- The number and percentage of responses will be presented in the form XX (XX.X).

- All p-values will be rounded to 4 decimal places. All p-values that round to 0.0000 will be presented as '<0.0001' and p-values that round to 1.0000 will be presented as '>0.9999'.
- All summary tables will include the analysis population sample size (i.e., number of subjects).
- Study Day 1 is defined as the date at which the subject receives the first application of the study drug. All study days are determined relative to Day 1. Relative days will be calculated as:

$$\text{Relative Day} = \text{Assessment Date} - \text{First Application Date} + 1.$$

- Baseline values will be defined as those values recorded closest to, but prior to, the study drug on Day 1 unless otherwise specified in the protocol.
- Change from baseline will be calculated as follows:

$$\text{Change} = \text{Post-baseline value} - \text{baseline value}.$$

- Date variables will be formatted as YYYY-MM-DD for presentation.
- Tables, figures, and listings will be presented in landscape orientation.
- SAS® Version 9.4 or higher will be the statistical software package used for all data analyses.
- All data from this study will be presented in a listing. All listings will be sorted by subject number and visit date, as applicable.
- Table and listing numbering will follow ICH guidelines for post-text table and listing numbering.

